Patients with electrical and chemical burns will be excluded, as will those with serious inhalation injury requiring treatment to maintain oxygen saturation. Patients in overt shock (defined as serum lactate >2.5 , or hypotension and altered mental status), Pregnant patients, psychiatrically unstable patients will be excluded.

Patients with oropharyngeal defects and/or previously known diagnoses leading to high risk of aspiration, and/or precluding safe nasal-enteric access will be excluded. Patients with history of chronic nausea and/or vomiting, including those with a diagnosis of gastroparesis due to diabetes mellitus will be excluded.

Patients with a Baux score of over 100 (age + TBSA), patients with declared palliative intent on admission, and patients for whom clinicians have high level of clinical concern based on clinical judgement will also be excluded.

Qualitative Component:

Inclusion Criteria

Healthcare workers (physicians, nurses, nursing assistants) who are anticipated to or have provided care to eligible patients in the enteral resuscitation arm of the study.

[figure not shown]
Exclusion Criteria

Exclusion criteria include co-PIs and co-investigators in this study to avoid bias.

11. Intervention

Please see schematic below for Intervention workflow. Specific goal-directed resuscitation protocols for IV fluid resuscitation and Enteral-based resuscitation in **Appendix** including details regarding modifications to allocated interventions based on response, patient request and improving/worsening disease.

Intervention Workflow Overview

General Resuscitation Protocol for Intravenous and Enteral-based Resuscitation

Resuscitation Timeline	Fluid Protocol	Clinical Assessment	Laboratory Assessment*	Additional Interventions
Hour 1	See Appendices A and B	Measure and record vital signs every two hours or more frequently as needed. (Temperature, blood pressure, heart rate, respirations, oxygen saturation), urine output, physical signs of overt shock	CBC, BMP, Lactate, PT/PTT/INR (15 mL)	Additional interventions such as colloid or blood product transfusion, vasoactive agents, escharotomy/ faschiotomy, intubation as deemed necessary by clinical care team will be noted throughout this time period.
Hours 2-7				
Hour 8	Administer Lactated Ringer's (LR) or Oral Rehydration Solution + LR according to calculated Parkland formula**		CBC, BMP, Lactate (10 mL)	
Hours 9-15				

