We will perform descriptive and comparative statistics for both qualitative and quantitative implementation metrics. Qualitative analysis of the patient and focus group interviews will use a template analysis approach to code and organize data for cross-case analysis of patterns of challenges and facilitators for each component of the resuscitation bundle.

21. Data Monitoring

The research team will conduct weekly virtual meetings (increasing frequency of meetings as needed) to discuss progress and relevant issues. We will measure against our internal timelines of progress, including enrolling 10 patients per month after enrollment begins. [name], study PI, and [name], study co-I, along with trained research assistants will be present for day to day monitoring, questions and problem solving. [name], U.S.- based PI will monitor all data submitted to RedCap for issues or patient safety concerns. [name], study co-I

and Assistant Professor of Surgery at University of Washington, will serve as a mentor for supervision and guidance on conducting the study.

Additionally, a Data Monitoring and Safety Board will be developed to monitor patient adverse events (AE) and serious adverse events (SAE). This is described below in section 22.

22. Harms

All patient clinical Adverse Events (AE) and Serious Adverse Events (SAE) will be monitored by study PIs. Furthermore, solicited or spontaneously reported adverse events will be reported to the study PIs. These will be investigated internally, in addition to reporting to the DSMB. All SAE will be reported to the DSMB within 1 working day of occurrence. All other AE and solicited or reported AE will be provided to the DSMB by study PI or Research Coordinator on a weekly basis.

Definitions:

Adverse Events (AE): are defined as those characterized as temporary in nature, mild symptomatology and no risk of long-term impact on morbidity and mortality, i.e. nausea/vomiting

Serious Adverse Event (SAE): those with risk of long-term impact on morbidity and mortality such as aspiration events, kidney injury requiring renal replacement therapy, and death.

Patients who experience serious adverse events attributed as a consequence of participation in the study may have costs of additional care (such as ventilation needs, renal replacement therapy needs) covered by the study.

23. Auditing

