Appendix A: Enteral resuscitation literature review with references

[figure not shown]
Enteral resuscitation is efficacious and has unique physiological benefits in animal models.

Multiple studies have demonstrated that sufficient volume repletion with enteral resuscitation can be achieved in burned animal models. Glucose-electrolyte solutions are well tolerated at rates commensurate with fluid resuscitation prediction formulas (i.e., evidence-based formulae that guides fluid resuscitation for burns, e.g., modified Brooke formula).¹

A research team at The U.S. Army Institute for Surgical Research (USAISR) randomized 18 burned Yorkshire swine to three resuscitation groups: fluid deprivation, ad libitum oral water, or 70 mL/kg/day

WHO ORS.² ORS intake increased urine output and was associated with a lower plasma creatinine (i.e., a biomarker for acute kidney injury) compared to ad libitum or no water (Figure 1). The findings suggested that enteral resuscitation with WHO ORS rescues kidney function following burn injury.

Figure 1: World Health Organization (WHO) Oral Rehydration Solution (ORS) increases urine output positively influences burn-induced biomarkers compared in a porcine burn model⁸

Caption for Figure 1: Total fluid intake (A) urine output volume (B), and (C) Average glomerular filtration rate (GFR) throughout the duration of the study. Levels of creatinine (D, E) and urea nitrogen in the plasma (F) and the urine (G). Urinary protein (H). Means \pm SEM with a different superscript are significantly different ($P < 0.05$) between treatments for indicated time point and a \dagger indicates a significant ($P < 0.05$) difference from the BL value.

Enteral resuscitation also has unique physiological benefits that are not achieved by IV resuscitation, including maintenance of intestinal mucosal integrity and reduction in intestinal mucosal edema characteristic of capillary leak syndrome after burn.³ Given that loss of intestinal mucosal integrity and bacterial byproduct translocation are hypothesized to contribute to multi-system organ failure, a common cause of death among burn patients, **enteral resuscitation may not only be a feasible and convenient complement to IV resuscitation, but may also be superior to IV resuscitation for patients with moderate-size burn injuries.**

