Target Urine Output: _____ kg x 0.5 ml/kg/hr = _____ per hour						Upper CutOff = _____ kg x 0.8 ml/kg/hr = _____ per hr Lower CutOff = _____ kg x 0.2 ml/kg/hr = _____ per hr			2 Hourly Urine Upper Cutoff: _____ ml Target: _____ ml Lower CutOff: _____ ml				
Resuscitation Start time: _____ : _____ AM / PM						Time post Incident: _____ Hrs _____ Mins							
Resus. Hour	Planned total fluid rate	AMOUNT OF FLUIDS GIVEN			Total fluids given (since last check)	Urine Output (q 2hrs)	VITALS		SYMPTOMS: ✓ if yes			Comments on symptoms or issues	CALCULATED RESUSCITATION FOR NEXT 2 HRS.
		Oral fluids		IV fluids			Additional fluids	Heart Rate	Blood Pressure	Oxygen Sat (%)	Nausea		
1 - 2						mL							
3 - 4						mL							
5 - 6						mL							
7 - 8						mL							
9 - 10						mL							
11 - 12						mL							

← Lower Cutoff

TARGET URINE OUTPUT

Upper Cutoff →

↑↑ Fluid by 20%

↑ Fluid by 10%

(continue same)

↓ Fluid by 10%

↓↓ Fluid by 20%

Resus. Hour	Planned total fluid rate	AMOUNT OF FLUIDS GIVEN			Total fluids given (since last check)	Urine Output (q 2hrs)	VITALS			SYMPTOMS: ✓ if yes				Comments on symptoms or issues	CALCULATED RESUSCITATION RATE FOR NEXT 2 HRS.			
		Oral fluids		IV fluids	Additional fluids		Heart Rate	Blood Pressure	Oxygen Sat (%)	Nausea	Vomiting	Distention	Reflux					
		By mouth	By NG															
13 - 14						ml												
15 - 16						ml												
17 - 18						ml												
19 - 20						ml												
21 - 22						ml												
23 - 24						ml												

Resuscitation Laboratory Results

Time of Resuscitation	CBC	BMP	Arterial Blood Gas	Coagulation Markers (PT/PTT/INR)
Admission	WBC: Hgb: Hct: Plt:	Na: K: BUN: Creat:	Lactate: Cl: HCO ₃ :	PT: PTT: INR:
Hour 8	WBC: Hgb: Hct: Plt:	Na: K: BUN: Creat:		
Hour 16	WBC: Hgb: Hct: Plt:	Na: K: BUN: Creat:		
Hour 24	WBC: Hgb: Hct: Plt:	Na: K: BUN: Creat:	Lactate: Cl: HCO ₃ :	PT: PTT: INR:
Hour 32	WBC: Hgb: Hct: Plt:	Na: K: BUN: Creat:		
Hour 40	WBC: Hgb: Hct: Plt:	Na: K: BUN: Creat:		
Hour 48	WBC: Hgb: Hct: Plt:	Na: K: BUN: Creat:	Lactate: Cl: HCO ₃ :	PT: PTT: INR:

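### The bedside chart prompts only for gastrointestinal symptoms and Section 22 names no IV-related harm, so any by-arm comparison of adverse events would be tilted against the enteral arm

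*Combined protocol and SAP*

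**What the plan says.** Section 22 (Harms) defines non-serious adverse events as "temporary in nature, mild symptomatology and no risk of long-term impact on morbidity and mortality, i.e. nausea/vomiting". It describes serious events by their risk of lasting harm, with the examples "such as aspiration events, kidney injury requiring renal replacement therapy, and death". It also provides that "solicited or spontaneously reported adverse events will be reported to the study PIs". Serious events go to the DSMB within one working day, and the others weekly.

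The Documentation Chart in Appendix B has a block headed "SYMPTOMS: ✓ if yes". Its columns, legible in the hours 13–24 half of the chart, are nausea, vomiting, distention and reflux. Beside them is a free-text column, "Comments on symptoms or issues". The chart also records oral, IV and additional fluids, the planned rate, urine output with cutoffs, heart rate, blood pressure and oxygen saturation.

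The Section 11 table adds that certain interventions are recorded, among them "escharotomy/ faschiotomy, intubation as deemed necessary by clinical care team will be noted throughout this time period". The same table gives the fluid as Lactated Ringer's or "Oral Rehydration Solution + LR according to calculated Parkland formula", so enteral patients can also receive IV fluid.

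Section 17 states that neither patients nor providers are blinded. Under Section 18, bedside nurses and clinicians complete the chart and research assistants transcribe it into REDCap. Section 20 plans descriptive and comparative statistics for implementation metrics and mentions no safety analysis.

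**The concern.** A symptom with its own box is asked about at every two-hourly check. An event without one is recorded only if someone thinks to write it down, report it, or treat it with an intervention that is noted. The prompted symptoms, and aspiration among the named serious events, are the harms one would expect mainly from fluid given by mouth or tube. The harms one would expect mainly from IV treatment (a failed or infiltrated line, fluid overload) are neither prompted nor named. The staff filling in the chart know the arm.

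The stated goal is to compare enteral resuscitation with IV standard of care, so the non-fatal, route-related harms are the ones most likely to separate the arms. If they are collected with different intensity, no later analysis can repair the difference. The DSMB would be reading the same uneven record week by week.

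**Working it through.** **1. Count of what is prompted and named.**

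- Chart tick boxes (Appendix B): 4 of 4 gastrointestinal, 0 of 4 IV-related.
- Events named in Section 22, counting nausea/vomiting as one: 2 of 4 gastrointestinal or aspiration, 2 of 4 possible in either arm (renal replacement, death), 0 of 4 IV-related.

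**2. Routes left open to an IV-related harm.** These are a spontaneous report, the comments column, oxygen saturation, fluid given against fluid planned, urine output against the upper cutoff, 8-hourly laboratory tests, and a noted intubation or fasciotomy. None is tied to an adverse event definition, and the noted interventions pick up only harm severe enough to need one. Capture is therefore lower than for a tick box, but above zero.

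**3. Size.** The plan gives no adverse event rate, so there is no stated figure to reproduce. All rates below are assumptions. The only input from the documents is 120 patients per arm (target 240, ratio 1:1).

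Assume gastrointestinal events in 20% (enteral) v 5% (IV), line/overload events in 5% v 15%, no overlap, full capture of gastrointestinal events, and a fraction c of line/overload events captured equally in both arms. Then, in percentage points:

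recorded gap = (20 + 5c) − (5 + 15c) = 15 − 10c

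| c | Enteral | IV | Gap | Patients of 120 |
|---|---|---|---|---|
| 1 (truth) | 25% | 20% | 5 points | 30 v 24 |
| 0.5 | 22.5% | 12.5% | 10 points | 27 v 15 |
| 0 | 20% | 5% | 15 points | 24 v 6 |

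The artefact is the recorded gap minus the true gap: (15 − 10c) − 5 = 10(1 − c). That is 5 points at c = 0.5 and 10 points at c = 0.

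**4. Dilution.** The 10 in that expression is the difference in line/overload rates between arms (15 − 5). If IV fluid in the enteral arm halves that difference to 5 points, the artefact halves too: 2.5 points at c = 0.5 and 5 points at c = 0. If the two arms had equal line/overload rates, it would vanish.

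**5. A second illustration, with equal true harm.** Suppose each arm has the same true risk p of its own route-related harm, and each harm is confined to its arm. The false gap is p × (capture of gastrointestinal events − capture of IV-related events).

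- p = 20%, capture 90% v 50%: 0.20 × 0.40 = 8 points (21.6 v 12.0 events of 120).
- p = 20%, capture 90% v 30%: 0.20 × 0.60 = 12 points (21.6 v 7.2 events).
- p = 10%: 4 and 6 points. p = 30%: 12 and 18 points.
- Equal capture: no gap at any p.

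The direction is the same throughout. The size depends entirely on the assumed rates and capture.

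**The case against.** The strongest reply is that the plan has other ways of catching IV harms. Section 22 covers all clinical adverse events and accepts spontaneous reports. Its serious-event list is open, so pulmonary oedema or compartment syndrome could qualify without being named. The chart and the intervention record hold relevant signs. This stands: a reader might infer that IV harms will be missed, and the documents do not support that. They support under-recording.

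Three other stronger readings also fail.

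- **A biased safety table is planned.** None is described. Section 20 covers implementation metrics only. The point concerns any comparison that is made, and the record the DSMB receives.
- **An advantage of enteral treatment cannot show.** It can. Hypothesis 2 concerns delays and interruptions, a failed line may show as a shortfall of fluid given against planned, and the Appendix C interview asks about difficulties with both routes.
- **Appendix A promises less oedema and the chart ignores it.** The Appendix A claim is a "reduction in intestinal mucosal edema characteristic of capillary leak syndrome after burn", made under a heading on animal models. A bedside box could not observe that, so it lends no support here.

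It is also fair to say that the split by arm is not clean. The gastrointestinal boxes appear on the chart for both arms, enteral patients may receive Lactated Ringer's, and Appendix B allows for an IV bolus in either arm. These facts dilute the tilt. They do not remove it as long as line and overload harms are commoner in the IV arm.

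Finally, the flowsheet figures and the REDCap form are not available to read, so a field may exist that cannot be seen. The chart and Section 22 are what can be judged.

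**Conclusion.** The point holds in a limited form. Gastrointestinal harms are prompted at each check and IV-related harms are neither prompted nor named, so the two would be ascertained unequally in an open-label trial and a by-arm comparison would lean against the enteral arm. Death and renal replacement are not affected in this way.

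The size cannot be stated from the documents. Under the first set of assumed rates, the distortion is 5 points at half capture and 10 at zero capture, on a true gap of 5. Zero capture is a limiting case, not an expectation. The conclusion rests on two assumptions: that prompted events are recorded more completely than unprompted ones, and that line/overload harms are commoner with IV treatment. It does not bear on the sample size or on the urine-output outcome. The change is cheap and worth making, because the data cannot be recovered afterwards.

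**What to change.** 1. Add tick boxes to the same two-hourly grid, and matching REDCap fields, for IV access failure or infiltration and for fluid-overload signs. The signs should be defined in advance by the clinical team, and the boxes completed at the same times in both arms.
2. Name these events in Section 22, and make clear that nausea/vomiting is an example and not the whole definition. State which interventions already noted, such as fasciotomy and intubation, count as adverse or serious adverse events.
3. Add to Section 20 a descriptive by-arm summary under two headings (gastrointestinal/aspiration; line/fluid-overload), with solicited and unsolicited events shown separately. Give the DSMB the same layout.

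The cost is two or three entries per check. Over the twelve two-hourly checks in the first 24 hours that is 2 × 12 = 24 to 3 × 12 = 36 entries per patient. Section 18 already leaves the chart open to adaptation. The side effect to manage is that Section 12 lists how completely the bedside record is filled in among its primary endpoint variables. The new columns should therefore be left out of that measure, or applied to it from a stated date. Patients charted before the change should be identified in the safety summary, because their line and overload events were not prompted. Treatment and sample size do not change.

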Appendix A: Enteral resuscitation literature review with references

[figure not shown]
Enteral resuscitation is efficacious and has unique physiological benefits in animal models.

Multiple studies have demonstrated that sufficient volume repletion with enteral resuscitation can be achieved in burned animal models. Glucose-electrolyte solutions are well tolerated at rates commensurate with fluid resuscitation prediction formulas (i.e., evidence-based formulae that guides fluid resuscitation for burns, e.g., modified Brooke formula).¹

A research team at The U.S. Army Institute for Surgical Research (USAISR) randomized 18 burned Yorkshire swine to three resuscitation groups: fluid deprivation, ad libitum oral water, or 70 mL/kg/day

WHO ORS.² ORS intake increased urine output and was associated with a lower plasma creatinine (i.e., a biomarker for acute kidney injury) compared to ad libitum or no water (Figure 1). The findings suggested that enteral resuscitation with WHO ORS rescues kidney function following burn injury.

Figure 1: World Health Organization (WHO) Oral Rehydration Solution (ORS) increases urine output positively influences burn-induced biomarkers compared in a porcine burn model⁸

Caption for Figure 1: Total fluid intake (A) urine output volume (B), and (C) Average glomerular filtration rate (GFR) throughout the duration of the study. Levels of creatinine (D, E) and urea nitrogen in the plasma (F) and the urine (G). Urinary protein (H). Means \pm SEM with a different superscript are significantly different ($P < 0.05$) between treatments for indicated time point and a \dagger indicates a significant ($P < 0.05$) difference from the BL value.

Enteral resuscitation also has unique physiological benefits that are not achieved by IV resuscitation, including maintenance of intestinal mucosal integrity and reduction in intestinal mucosal edema characteristic of capillary leak syndrome after burn.³ Given that loss of intestinal mucosal integrity and bacterial byproduct translocation are hypothesized to contribute to multi-system organ failure, a common cause of death among burn patients, **enteral resuscitation may not only be a feasible and convenient complement to IV resuscitation, but may also be superior to IV resuscitation for patients with moderate-size burn injuries.**

Appendix B: Resuscitation Protocol Flowsheets and Documentation Chart

Enhanced Adult Burn Fluid Resuscitation Protocol for Intravenous Fluid Only Resuscitation

Use for Adults ≥ 18 years, not for pediatric patients, electrical/chemical burn patients or patients with suspected inhalation injury

- Baseline fluid calculation per Parkland Formula ($4\text{cc} \times \% \text{ TBSA} \times \text{weight (kg)} = 24\text{-hour fluid volume}$)
- Vital signs including Heart Rate (HR), Blood Pressure (BP), O₂ saturation and Urine Output (UO) should be tracked every 1 to 2 hours, with fluid rate adjusted accordingly
- **Target Urine Output = 0.5 mL/kg/hr; HR < 120 bpm; Systolic BP >90 mmHg**
- If hypotensive with EITHER Intravenous or enteral-based resuscitation, give bolus of 10cc/kg IV fluids. Consider vasopressor or colloid augmentation.
- For all calculated hourly resuscitation volumes, please round to the nearest 10 (i.e., 74 =70ml, 76=80mL)

[figure not shown]

Adult Burn Fluid Resuscitation Protocol for Enteral-based Resuscitation

Use for Adults ≥ 18 years, not for pediatric patients, electrical/chemical burn patients or patients with suspected inhalation injury

- Vital signs including Heart Rate (HR), Blood Pressure (BP), O₂ saturation and Urine Output (UO) should be tracked every 1 to 2 hours, with fluid rate adjusted accordingly
- Goal: UO=0.5 mL/kg/hr, HR < 120, Systolic BP >90
- If hypotensive with EITHER resuscitation type, give bolus of 10cc/kg IV fluids. Consider vasopressor or colloid augmentation.
- ORS can be administered by drinking or administering the calculated volume via NGT every hour
- For all calculated hourly resuscitation volumes, please round to the nearest 10 (ie 76=80mL)

Abbreviations: IV= Intravenous, RL= Ringer's Lactate, ORS= Oral Rehydration Solution, NGT= Nasogastric Tube

Today's Date: / / 2021			Date and Time of Injury: / / 2021; : AM/PM			InPatient No:							
Name		Admission Wt. (kg)	%TBSA (Do not include superficial 1 st degree burn)			Burn Mechanism							
Parkland Formula: Total Resuscitation Volume: _____ % X _____ kg X 4ml = _____ in 24 hours (TBSA) (pt. weight)						First 8 hours (use 1/2 of total volume) _____ ÷ 8 hrs. Starting Hourly Fluids = _____ ml/hour			Starting 2 Hourly I.V Fluid _____ ml				
Target Urine Output: _____ kg x 0.5 ml/kg/hr = _____ per hour						Upper CutOff = _____ kg x 0.8 ml/kg/hr = _____ per hr Lower CutOff = _____ kg x 0.2 ml/kg/hr = _____ per hr			2 Hourly Urine Upper Cutoff: _____ ml Target: _____ ml Lower CutOff: _____ ml				
Resuscitation Start time: _____ : _____ AM / PM						Time post Incident: _____ Hrs _____ Mins							
Resus. Hour	Planned total fluid rate	AMOUNT OF FLUIDS GIVEN			Total fluids given (since last check)	Urine Output (q 2hrs)	VITALS		SYMPTOMS: ✓ if yes			Comments on symptoms or issues	CALCULATED RESUSCITATION FOR NEXT 2 HRS.
		Oral fluids		IV fluids			Additional fluids	Heart Rate	Blood Pressure	Oxygen Sat (%)	Nausea		
1 - 2						mL							
3 - 4						mL							
5 - 6						mL							
7 - 8						mL							
9 - 10						mL							
11 - 12						mL							

← Lower Cutoff

TARGET URINE OUTPUT

Upper Cutoff →

↑↑ Fluid by 20%

↑ Fluid by 10%

(continue same)

↓ Fluid by 10%

↓↓ Fluid by 20%

Resus. Hour	Planned total fluid rate	AMOUNT OF FLUIDS GIVEN			Total fluids given (since last check)	Urine Output (q 2hrs)	VITALS			SYMPTOMS: ✓ if yes				Comments on symptoms or issues	CALCULATED RESUSCITATION RATE FOR NEXT 2 HRS.			
		Oral fluids		IV fluids	Additional fluids		Heart Rate	Blood Pressure	Oxygen Sat (%)	Nausea	Vomiting	Distention	Reflux					
		By mouth	By NG															
13 - 14						ml												
15 - 16						ml												
17 - 18						ml												
19 - 20						ml												
21 - 22						ml												
23 - 24						ml												

Resuscitation Laboratory Results

Time of Resuscitation	CBC	BMP	Arterial Blood Gas	Coagulation Markers (PT/PTT/INR)
Admission	WBC: Hgb: Hct: Plt:	Na: K: BUN: Creat:	Lactate: Cl: HCO ₃ :	PT: PTT: INR:
Hour 8	WBC: Hgb: Hct: Plt:	Na: K: BUN: Creat:		
Hour 16	WBC: Hgb: Hct: Plt:	Na: K: BUN: Creat:		
Hour 24	WBC: Hgb: Hct: Plt:	Na: K: BUN: Creat:	Lactate: Cl: HCO ₃ :	PT: PTT: INR:
Hour 32	WBC: Hgb: Hct: Plt:	Na: K: BUN: Creat:		
Hour 40	WBC: Hgb: Hct: Plt:	Na: K: BUN: Creat:		
Hour 48	WBC: Hgb: Hct: Plt:	Na: K: BUN: Creat:	Lactate: Cl: HCO ₃ :	PT: PTT: INR:

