Hour 16	Add or subtract fluid volume by every 2 hours based on urine output goal of at least 0.5 mL/kg/hr.		CBC, BMP, Lactate (10 mL)	
Hours 16+	IV Metoclopramide to be administered if GI symptoms such as bloating, nausea, discomfort, vomiting.		CBC, BMP, Lactate every 8 hours, and PT/PTT/INR every 24 hours until resuscitation complete.	

* CBC=Complete blood count; BMP=Basic metabolic panel; PT=Prothrombin time; PTT=Partial Thromboplastin time; INR=international normalized ratio

**Parkland formula= $4\text{cc} * \% \text{ Total Body Surface Area burned(TBSA)} * \text{weight(kg)} = 24 \text{ hour fluid volume}$
Total resuscitation volume divided by 2, then divided by 8 to determine the starting resuscitation volume.

12. Outcomes

Goals

The overarching goals are to understand challenges and facilitators of enteral-based resuscitation and understand the effectiveness of the technique compared to standard of care (intravenous resuscitation).

Specific Aim 1: Determine the frequency of adherence to the enteral-based and IV fluid resuscitation protocols, and determine frequency of successful resuscitation.

Hypothesis 1: With goal-directed resuscitation, the primary outcomes of goal average urine output and successful resuscitation will be achieved in the majority of patients (over 50%). Protocol adherence will be at least 50%.

Specific Aim 2: Describe the challenges and facilitators to enteral and IV resuscitation protocol acceptance, implementation, compliance and sustainability.

Hypothesis 2: Enteral resuscitation will have logistical advantages over IV resuscitation, reduce delays in the initiation of resuscitation, have fewer interruptions, and will be easier to implement.

Primary endpoints

For the quantitative aspect, study variables will include measures of implementation and adherence to the enteral resuscitation protocol with variables such as: percent of resuscitation conducted enterally, proportion of protocol laboratory and clinical assessments completed, completeness of bedside documentation, number of inappropriate adjustments of resuscitation fluid rates based on urine output.

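### The Documentation Chart records no actual time for checks or blood draws, so the adherence measures cannot separate on-time from late checks or wrong fluid adjustments from timing artefacts

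*Combined protocol and SAP*

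**What the plan says.** Section 12 lists, under primary endpoints, the "proportion of protocol laboratory and clinical assessments completed" and a count of fluid-rate changes judged inappropriate against urine output. It gives no timing window for either. Hypothesis 1 expects protocol adherence of at least 50%.

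On the checking interval, the General Resuscitation Protocol table in Section 11 says "Measure and record vital signs every two hours or more frequently as needed". Both arm-specific protocols in Appendix B say observations "should be tracked every 1 to 2 hours, with fluid rate adjusted accordingly".

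The Documentation Chart (Appendix B) has preprinted two-hour rows, from hours 1-2 to hours 23-24. Its columns cover planned rate, fluids by route, "Total fluids given (since last check", "Urine Output (q 2hrs", vital signs, symptoms, comments and the fluid calculated for the next two hours. The header gives hourly figures (target "kg x 0.5 ml/kg/hr", upper cutoff "kg x 0.8 ml/kg/hr", lower cutoff at 0.2 mL/kg/h) and two-hour volumes derived from them, beginning with "2 Hourly Urine Upper Cutoff". Changes of 10% or 20% in fluid are keyed to these cutoffs. The laboratory table is labelled admission, hour 8, hour 16 and so on.

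The only clock times on the chart are those of injury and of the start of resuscitation. Section 18 states that the chart is transcribed into REDCap and may be adapted further.

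**The concern.** A urine volume becomes a rate only when divided by the time over which it was collected. The chart records the volume, assumes two hours, and does not record the actual interval. The protocol allows intervals to vary, and Section 9 describes a site with scarce resources and frequent delays, so unequal intervals should be expected.

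Two listed measures depend on this:

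- **Assessments completed.** A row filled on time, one filled late and one filled in afterwards look identical.
- **Inappropriate adjustments.** A change that follows a reading distorted by timing cannot be told from one that follows the patient's true urine rate. A genuine error can likewise look correct.

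The trial is unblinded and compares implementation between arms. If timeliness differed by arm, these data could not show it.

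**Working it through.** **Cutoffs.** The header's hourly figures, multiplied by 2, give two-hour volumes of 0.2 × 2 = 0.4, 0.5 × 2 = 1.0 and 0.8 × 2 = 1.6 mL/kg. The header is consistent with itself. The sample size of 212 is not involved in this point.

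**Effect of the interval.** With true rate u (mL/kg/h) and actual interval T (h), the volume is u × T. Read against two-hour cutoffs, the apparent rate is u × T / 2.

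- u = 0.50, T = 2.5: 0.50 × 2.5 / 2 = 0.625.
- u = 0.50, T = 3: 0.50 × 3 / 2 = 0.75.
- u = 0.40, T = 3: 0.40 × 3 / 2 = 0.60. The reading has crossed the 0.5 target.
- A patient at 0.50 reads as the upper cutoff when T = 2 × 0.8 / 0.5 = 3.2 h.

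**How often this changes the chart step.** The documents give no lateness data and no width for the no-change band around the target, so the following are assumptions:

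- The true rate is steady for each patient, spread uniformly over 0.2-0.8.
- Checks are due every 2 h, and each is late by a uniform amount d from 0 to a maximum D. Hence T = 2 + d(this check) − d(previous check), with no lateness at the start.
- The chart's five steps are read as +20% below the lower cutoff, +10% up to the target band, no change, −10% up to the upper cutoff, and −20% above it.
- The no-change band is 0.45-0.55, 0.40-0.60 or 0.35-0.65.

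Simulated results (200,000 patients × 12 rows), range over the three bands:

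| Maximum lateness D | Row points to a different step | Same, ignoring 10% versus 20% in one direction | Opposite direction |
|---|---|---|---|
| 30 min | about 22% | about 14% | at most 0.1% |
| 60 min | 39-41% | 26-28% | at most 3.8% |

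At D = 15 min about 11% of rows differ. The opposite-direction maxima come from the narrowest band tried; a narrower one would give more.

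**Sensitivity to the band.** For a patient exactly at 0.50, a band of 0.50 ± w is left when T departs from 2 h by more than c = 4w. The chance is 1 − c/D in the first row and (1 − c/D)² in the other eleven.

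- D = 1 h, band 0.45-0.55 (c = 0.2): (11 × 0.64 + 0.80) / 12 = 65%.
- D = 1 h, band 0.40-0.60 (c = 0.4): (11 × 0.36 + 0.60) / 12 = 38%.
- D = 1 h, band 0.35-0.65 (c = 0.6): (11 × 0.16 + 0.40) / 12 = 18%.
- D = 0.5 h: 38%, 5% and 0% for the same three bands.

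This figure depends too heavily on the unstated band to be quoted as one number.

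**24-hour total.** Lateness within the day cancels; only the last check matters. Mean inflation is (D/2)/24: 0.25/24 = 1.0%, 0.50/24 = 2.1% and 0.75/24 = 3.1% for D = 30, 60 and 90 min.

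**The case against.** The strongest objection is that the outcome behind the sample size, 24-hour urine output in the target range (Section 14), is hardly touched. That stands. A reader might infer from the missing times that this outcome is unreliable; a shift of about 1-3% does not support that.

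Other stronger readings also fail:

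- **Late checks count as completed, so adherence is overstated.** The plan has no scoring rule. Section 12 speaks of completion, not punctuality, and a late check that was done is arguably complete. What stands is that the data could not support a timeliness measure.
- **A permitted one-hour check would be misread by half.** The header also prints hourly cutoffs, and two hourly volumes can be summed in one two-hour row. The form largely answers this example, though it neither asks for nor records the interval used.
- **The enteral arm needs hourly staff contact, so timeliness must differ by arm.** Appendix B lets patients drink the solution, and the two-hourly checks apply to both arms. A difference by arm is possible, not shown.
- **The times are lost for good.** The REDCap form is not among the documents, the chart stays in the medical record (Section 19), and research assistants are present daily (Section 21). Some times might be found elsewhere, but no such source is described.

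In the copy available, the flowsheet figures are absent and the heading of the first half of the grid is partly broken. The second half reads as complete and has no time column.

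Finally, an inappropriate adjustment could mean simply a departure from the charted reading. On that definition the interval matters less, but the plan does not say which definition it uses.

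**Conclusion.** The point holds as a limitation of the adherence data, worth correcting but not a threat to the 24-hour urine outcome. As described, the chart cannot separate on-time, late and back-filled checks, nor a wrong adjustment from one driven by the collection interval.

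The arithmetic linking reading to interval is exact. The frequencies (about 22% or 39-41% of rows, with opposite-direction steps at most 0.1% or 3.8%) rest on assumed lateness of 0-30 or 0-60 minutes, steady true rates and an assumed no-change band. They show what modest lateness could do, not what happens at this site. The documents do not establish that adherence will be overstated or that the arms will differ.

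**What to change.** 1. Add an actual-time field to every two-hourly row and a draw time to every laboratory row, and carry both into REDCap.
2. In Section 12, define an assessment as completed on schedule if made within a prespecified window of its due time. Report on-time, late and missed checks by arm.
3. In Section 20, state that urine rate will be volume divided by weight and actual elapsed hours when adjustments are classified for analysis, and define an inappropriate adjustment.
4. Reconcile the interval wording in Section 11 and the Appendix B protocols with the fixed two-hour chart. Any bedside titration rule is for the investigators to settle.

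The cost is one time entry per check or draw, the matching REDCap fields and a few sentences in the plan. Section 18 already allows the form to be adapted. Reported on-time adherence may be lower than a plain count of filled rows. The change should precede further data collection, because analysis cannot rebuild times that were never written down.
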